## 10. Determination of Sample Size

The sample size calculation can be found in section 9.4 of the protocol.

## 11. Study Framework

The overall objective for each of the study outcomes is to compare Transforaminal Epidural Steroid Injection (TFESI) with surgical microdiscectomy for superiority.

## 12. Confidence Intervals, p-values and Multiplicity

All applicable statistical tests will be two-sided and will be performed using a 5% significance level; 95% confidence intervals will be presented. No adjustment will be made for multiplicity for the secondary outcomes.

## 13. Timing and Objectives of Interim and Final Analyses

### 13.1. Interim monitoring and analyses

Details on interim analyses are compatible with those found in the protocol in section 9.5. The IDSMC met at least annually to review the accumulated data. Details can be found in the Statistical Analysis Plan: Internal Pilot version 1.0 dated 09/07/15.

### 13.2. Final analysis

The final analysis for all outcomes will be analysed after the end of the trial, which is defined in section 8.7 of the protocol as “the date on which data for all participants is frozen and data entry privileges are withdrawn from the trial database”.

## 14. Disposition of Participants

### 14.1. Screening, eligibility and recruitment

Screening logs will be summarised by site in a table detailing:

- i) the number of patients who were assessed for eligibility at the screening visit,
- ii) those who met the study inclusion criteria at screening (expressed as a frequency and a % with the denominator being i),
- iii) those who did not meet the study inclusion criteria at screening (expressed as a frequency and a % with the denominator being i),
- iv) those who were eligible at screening and consent obtained, (expressed as a frequency and a % with the denominator being ii),
- v) those who were eligible at screening and consent not obtained, (expressed as a frequency and a % with the denominator being ii),
- vi) those who provided consent but were not randomised (expressed as a frequency and a % with the denominator being iv),
- vii) those who provided consent and were randomised (expressed as a frequency and a % with the denominator being iv),

Reasons for ineligibility will be summarised by site and overall in a table with reasons. Frequencies will be presented along with percentages using the denominator as iii).

Reasons for consent declined will be summarised by site and overall in a table using categories. Frequencies will be presented along with percentages using the denominator as v).

A recruitment summary table will be presented showing the following for each centre: centre code, hospital name, dates site opened/closed to recruitment, dates of first/last randomisation and total number randomised.

#### 14.2. **Post randomisation discontinuations**

Ideally, patients that decide to withdraw from treatment prior to treatment will remain in the study for follow-up. However, patients could decide to withdraw from the trial completely.

Withdrawals will be presented as line listings detailing:

- Randomisation number
- Date of withdrawal
- Date of visit
- Date of discontinuation and whether before/after treatment
- Level of withdrawal
- Who made the decision to withdraw the participant from the trial
- How many injections the participant has received (if applicable)
- Reason for discontinuation

## 15. **Protocol Deviations**

Protocol deviations to be reported can be found in section 6 of the trial monitoring plan (V2.0 dated 25/01/2018).

## 16. **Unblinding**

Not applicable as NERVES is an open label study.

## 17. **Efficacy Evaluations**

### 17.1. **Data Sets Analysed**

The principle of intention-to-treat, as far as practically possible, will be the main strategy of the analysis adopted for the primary outcome and all the secondary outcomes. These analyses will be conducted on all randomised participants, in the group to which they were allocated, and for whom the outcome(s) of interest have been observed/measured.

The membership of the analysis set for each outcome will be determined and documented and reasons for participant exclusion will be given.

## 17.2. Demographic and Other Baseline Characteristics

The following patient baseline data will be presented:

- Gender (male/female)
- Age (EudraCT categories: Adolescents (12-17 years/ Between 18 and 65 years/ 65 years to 84 years)
- Whether the participant is of reproductive potential (yes/no)
- Whether the patient is currently taking coagulant medication (yes/no)
- Whether the patient has previously had surgery at the same intervertebral disc (level) (yes/no)
- How many weeks the patient has experience leg pain symptoms for
- Whether the patient has used medication to help treat pain and symptoms (yes/no)
- Whether the patient has modified daily activities to help pain and symptoms (yes/no)
- Whether the patient has attended physiotherapy to help pain and symptoms (yes/no)
- Whether the patient has had other conservative (non operative) treatment to help pain and symptoms (yes/no)
- Estimated volume of canal occupied by disc prolapse as shown on MRI scan (Less than 25%/ Between 25-50%/Greater than 50%)
- Weight (kg)
- Height (cm)
- Posture (normal/abnormal)
- Range of movement (normal/abnormal)
- Muscle strength (normal/abnormal)
- Ankle jerks present (left/right/yes/no)
- Knee jerks present (left/right/yes/no)
- SLR reduction present (yes/no)
- Whether the patient has any other abnormalities (yes/no)
- Whether the patient is currently employed (yes/no)
- Whether the patient is currently unable to attend work due to sciatica (yes/no)
- Whether the patient is currently taking analgesics, steroids or anticoagulant medication (yes/no)

The above baseline values can be found on CRF “Form 1: Baseline & Eligibility”. For continuous variables the mean, SD, minimum, median, maximum and IQR will be presented to 1 decimal place.

### 17.3. Compliance with treatment

See section 8.1 of the NERVES trial protocol for definition of treatment compliance. The number and percentage of patients complying with treatment overall and by centre split by treatment group will be summarised.

### 17.4. Analysis of outcomes

All values for each outcome will be presented to 2 decimal places with the exception of p-values which will be presented to 3 decimal places.

#### 17.4.1 Primary Outcome

Oswestry Disability Questionnaire (ODQ) at 18 weeks ( $\pm 6$  weeks) (approximately 3 months post intervention).

##### 17.4.1.1 Derivation

###### Missing completion dates

For the primary outcome analysis, we need to know if the ODQ was completed within the protocol specified window (18  $\pm$  6 week post randomisation). If the date is missing then the date should be estimated as follows:

- If the questionnaire is from a face-to-face follow up visit (W18, W54) and if the variable FBK1CMPC='Yes' (NERVES questionnaire (Booklet 1) completed by the patient?) then the date of the visit is taken as the date of questionnaire completion.
- If the above was not the case but there is a completed booklet 1, then the date will be estimated as the midpoint between the date the questionnaire was provided to the patient and the latest possible date receipt of the CRF at the CTU. This can be expressed as:

$$\text{Completion Date} = \text{Date provided} + \frac{\text{Date received} - \text{Date provided}}{2}$$

- If the date is entered onto the questionnaire but is before the randomisation date (except for baseline questionnaires) then this should be imputed as above.

Note: If there are duplicate CRFs then the latest of these dates will be used.

Scoring

Scores from the ODQ can be found in patient questionnaire booklet 1. Scores will be calculated following the guidelines outlined in [10]. Scores are obtained as follows.

*Step 1: Recode the 10 ODQ items*

Items 1-10 on the ODQ will be recoded as in Table 17.4.1.1(a).

*Step 2: Calculate the overall score (%)*

$$\text{Overall ODQ score} = \frac{\text{Sum of the score of each of the applicable items with a non missing answer}}{\text{Maximum possible score}} \times 100$$

(Where the maximum possible score is based on the number of questions answered.)

*Step 3: Interpret the overall score (%)*

Interpreted as in Table 17.4.1.1(b)

Note: If a patient has not completed the questionnaire at  $18 \pm 6$  weeks post randomisation or has answered less than 8 out of 10 questions (including item 8), then the patient should be excluded from the analysis.

**Table 17.4.1.1(a): ODQ Recoding items**

Item no (MACRO variable)	Recoding
ODQS01C	0 = I have no pain at the moment. 1 =The pain is very mild at the moment. 2 =The pain is moderate at the moment. 3 =The pain is fairly severe at the moment. 4 = The pain is very severe at the moment. 5 =The pain is the worst imaginable at the moment.
ODQS02C	0 = I can look after myself normally without causing extra pain. 1 = I can look after myself normally but it is very painful. 2 = It is painful to look after myself and I am slow and careful. 3 = I need some help but manage most of my personal care. 4= I need help every day in most aspects of self-care.

	5 = I do not get dressed, wash with difficulty and stay in bed.
ODQS03C	
0 = I can lift heavy weights without extra pain.
 
1 = I can lift heavy weights but it gives extra pain.
 
2 = Pain prevents me from lifting heavy weights off the floor but I can manage if they are conveniently positioned.
 
3 = pain prevents me from lifting heavy weights but I can manage light to medium weights if they are conveniently positioned.
 
4 = I can lift only very light weights.
 
5 = I cannot lift or carry anything at all.

ODQS04C	
0 = Pain does not prevent me walking any distance.
 
1 = Pain prevents me walking more than one mile.
 
2 = Pain prevents me walking more than a quarter of a mile.
 
3 = Pain prevents me walking more than 100 yards.
 
4 = I can only walk using a stick or crutches.
 
5 = I am in bed most of the time and have to crawl to the toilet.

ODQS05C	
0 = I can sit in any chair as long as I like.
 
1 = I can sit in my favourite chair as long as I like.
 
2 = Pain prevents me from sitting for more than 1 hour.
 
3 = Pain prevents me from sitting for more than half an hour.
 
4 = Pain prevents me from sitting for more than 10 minutes.
 
5 = Pain prevents me from sitting at all.

ODQS06C	
0 = I can stand as long as I want without extra pain.
 
1 = I can stand as long as I want but it gives me extra pain.
 
2 = Pain prevents me from standing for more than 1 hour.
 
3 = pain prevents me from standing for more than half an hour.
 
4 = Pain prevents me from standing for more than 10 minutes.
 
5 = Pain prevents me from standing at all.

ODQS07C	
0 = My sleep is never disturbed by pain.
 
1 = My sleep is occasionally disturbed by pain.
 
2 = because of pain I have less than 6 hours sleep.

	
3 = Because of pain I have less than 2 hours sleep.
 
4 = Because of pain I have less than 2 hours sleep.
 
5 = Pain prevents me from sleeping at all.

ODQS08C	
0 = My sex life is normal and causes no extra pain.
 
1 = My sex life is normal but causes some extra pain.
 
2 = My sex life is nearly normal but is very painful.
 
3 = My sex life is severely restricted by pain.
 
4 = My sex life is nearly absent because of pain.
 
5 = Pain prevents any sex life at all.

ODQS08NC	
1 = Section 8 is not applicable to me.

ODQS09C	
0 = My social life is normal and causes me no extra pain.
 
1 = My social life is normal but increases the degree of pain.
 
2 = Pain has no significant effect on my social life apart from limiting my more energetic interests.
 
3 = Pain has restricted my social life and I do not go out as often.
 
4 = Pain has restricted social life to my home.
 
5 = I have no social life because of pain.

ODQS10C	
0 = I can travel anywhere without pain.
 
1 = I can travel anywhere but it gives extra pain.
 
2 = pain is bad but I manage journeys over two hours.
 
3 = pain restricts me to journeys of less than one hour.
 
4 = pain restricts me to short necessary journeys under 30 minutes.
 
5 = Pain prevents me from travelling except to receive treatment.

**Table 17.4.1.1(b): ODQ Interpretation**

The ODQ overall percentage corresponds to the categories below.

0% to 20%: Minimal disability	The patient can cope with most living activities. Usually no treatment is indicated apart from advice on lifting sitting and exercise.
21% to 40%: Moderate disability	The patient experiences more pain and difficulty with sitting, lifting and standing.

	Travel and social life are more difficult and they may be disabled from work. Personal care, sexual activity and sleeping are not grossly affected and the patient can usually be managed by conservative means.
41% - 60%: Severe disability	Pain remains the main problem in this group but activities of daily living are affected. These patients require a detailed investigation.
61%-80%: Crippled	Back pain impinges on all aspects of the patient's life. Positive intervention is required.
81%-100%	These patients are either bed-bound or exaggerating their symptoms.

#### **17.4.1.2 Analysis**

ODQ score at 18 weeks post-randomisation will be compared between groups using a linear regression model, adjusting for the stratification variable centre, treatment group and baseline ODQ score. The mean(SD) ODQ score at baseline and 18 weeks will be presented. The mean difference and 95% CI in ODQ at 18 weeks will be presented along with a p-value for the treatment covariate at 18 weeks. Model assumptions will be tested by checking for normality.

#### **17.4.2 ODQ at 30, 42 and 54 weeks after randomisation**

##### **17.4.2.1 Derivation**

Derivation details, including details on how to derive missing questionnaire completion dates, can be found in section 17.4.1.1.

##### **17.4.2.2 Analysis**

Change from baseline summary statistics (Total [n], Mean, SD, median, interquartile range, minimum and maximum) will be presented split by treatment arm at four key time-points(T18, T30, T42 and T54) using visit windows as specified in the protocol. Only data from scheduled visits at these time-points will be included within the summary statistics.

A repeated measures random effects model will be fitted. The dependent variable will be post baseline ODQ. Covariates will be: baseline ODQ, treatment arm, time (fitted as a continuous

variable), and a time-treatment arm interaction. Centre will be fitted as a random effect. The time-treatment interaction can be dropped if it is found to be non-significant ( $p < 0.05$ ).

If the model contains a time-treatment interaction, the mean (SD) ODQ for each treatment arm and the mean difference between treatment arms in ODQ will be estimated from the model, for each key time-point (T30, T42 and T54), together with a 95% CI.

If the model contains no interaction, the treatment effect (estimated mean difference in ODQ) will be reported together with a 95% CI and a p-value.

Note: whilst the study design defines ODQ to be measured at specific time-points, measurements that are not taken at per-protocol time-points may be included in this mixed model analysis.

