#### Previous studies of microdiscectomy for sciatica

Recent data from Peul et al (3, 6) suggests that surgical microdiscectomy may effectively relieve sciatica in 90% of patients with acute sciatica. This is comparable to favourable outcomes from conservative management of the condition at 12 months follow up. This above finding would suggest that there is a period of spontaneous resolution for this condition within the first 12 months of symptom onset, though surgical intervention could lead to quicker recovery. Treatment may be needed for patients in the acute phase of their condition and to prevent their symptoms from becoming chronic and resistant to treatment/intervention.

Surgery to remove a prolapsed lumbar intervertebral disc (PID) is regarded as the gold-standard treatment for acute sciatica. Adverse events are reported in up to 3% of operations and include the same spectrum of complications as SNRI but also death, paraplegia, sexual/bladder dysfunction and spinal fluid leak. Approximately 6% of operated herniated discs can recur and require re-operation (14). The long-term deleterious effects of this operation upon the patient are unknown. Specialist centres in the UK can carry out more than 500 primary microdiscectomy operations per year for this condition. The average length of stay for this procedure is two nights in hospital.

The advantages of microdiscectomy are:

- a) It has the highest reported success rate, working in 9 out of 10 patients.

Disadvantages are:

- a) It is expensive, requiring hospital admission.
- b) There are resource implications given that the skill level required to perform the procedure is high, requiring a consultant spinal surgeon (orthopaedic or neurosurgical surgeon) or their equivalent.
- c) It carries the highest level of morbidity/risk of all treatments.
- d) The long term consequences of surgical microdiscectomy are largely unknown.

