### 9.4 Sample Size

The primary outcome measure of Oswestry Disability Questionnaire (ODQ) has over thirty years of validation and is supported by OMERACT for low back pain research. Deyo et al (15) has recommended the use of ODQ as part of the core outcome measures for low back research. This outcome measure is supported by OMERACT in low back research. The scale ranges from 100 (extreme disability) to zero (extreme ability). A change of 10 points has been widely regarded in the literature as the minimal clinical significance. One study (16) specifically addressing this issue has suggested a range of 10.5 to 15 as clinically important. ODQ has over 30 years of validated, published data pertaining to low-back pathology and radicular symptoms. It has formed the basis for previous HTA trials exploring sciatica and will allow useful comparisons to be made to previous data.

In order to detect a difference between the two groups of 10 points on the ODQ at a 5% significance level with 90% power, a total of 172 participants are required. This assumes a standard deviation of 20 points based on a similar population in previous published trials (9, 15-18). The previous large and well-carried out WEST study based in the UK, suggested baseline ODQ SD between 16-18 (9). We have collected baseline ODQ data on 11 potentially eligible patients from the fast track sciatica clinic at the Walton Centre and this generated a standard deviation of 14.4, well under the assumed value. We will aim to recruit a target of 200 patients to allow for a 10% rate of missing outcome data. Of the 7 centres involved, allowing for one to have difficulties opening, this would then require recruitment of 30 patients in total from each participating centre and 50 patients from the lead centre. Potential recruitment populations could be as high as 500 patients per centre per year (based on HES data from numbers of lumbar microdiscectomies performed). Even assuming 50% ineligibility and 40% consent, this low rate of 30 patients per centre per year is realistic. The standard deviation used in this calculation will be checked after approximately 30 patients have been randomised and provided primary outcome data. This blinded internal pilot will not have any significant impact on the final analysis (19).

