#### **17.4.3.2 Analysis**

For this outcome see section 17.4.2.2 for analysis details. In addition to this, effect estimates, 95% CIs and a p-value at T18 should be reported.

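### The SAP's mixed model for five secondary outcomes has a self-contradictory rule for dropping the interaction, restricts time to a straight line, and leaves the within-participant covariance unstated

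*SAP*

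**What the plan says.** SAP 17.4.2.2 fits one model to all post-baseline ODQ scores and calls it a repeated-measures random-effects model. Three parts of it matter here.

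- **Drop rule.** "The time-treatment interaction can be dropped if it is found to be non-significant", followed in brackets by p < 0.05. If the interaction stays, differences are estimated at weeks 30, 42 and 54. If it goes, a single treatment effect is reported.
- **Time.** The covariates after baseline ODQ run "treatment arm, time (fitted as a continuous" variable), then the time-by-treatment interaction. No curvature term is listed.
- **Random effects.** "Centre will be fitted as a random effect". No participant effect and no residual covariance structure is given.

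SAP 17.4.3.2, 17.4.4.2, 17.4.6.2 and 17.4.7.2 apply the same model to leg pain, back pain, Roland-Morris and COMI, and add that "effect estimates, 95% CIs and a p-value at T18 should be reported". Protocol 4.2 lists ODQ at 30, 42 and 54 weeks as secondary endpoints. Week-18 ODQ, the primary outcome, has its own linear regression in SAP 17.4.1.2.

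**The concern.** The word and the inequality in the drop rule point in opposite directions, so two programmers could implement opposite rules.

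Reversing the inequality does not settle the matter. A non-significant interaction test is weak evidence that the effect is constant, yet it would decide whether endpoints at three separate times are reported as such or merged into one average. That average includes week 18, which is not one of the secondary ODQ time points. For the four other outcomes, a model without the interaction gives the same effect at every visit, so it has no week-18 estimate of its own. The SAP names no other model to supply one.

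The straight line and the unstated covariance add to this. The first can shift estimates between visits. The second, if taken literally, affects both the interval widths and the interaction test on which the drop rule depends. Independent programming under SAP 21 covers the primary analysis and safety data only, so it would not catch a mis-specified secondary model.

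**Working it through.** **Inputs from the documents.** SAP 12: "All applicable statistical tests will be two-sided and will be performed using a 5% significance level; 95% confidence intervals will be presented". Protocol 9.4: "10 points on the ODQ at a 5% significance level with 90% power, a total of 172 participants are required", for which the SD is taken as 20. Protocol 9.4.2: baseline-to-follow-up correlation 0.49, 66 per group, 148 in total after 10% loss. SAP 17.4.2.2: four visits, 12 weeks apart.

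**Assumptions.** The documents do not give the correlation rho between follow-up scores within a participant (given baseline); 0.49 is a different quantity. I use rho = 0.3, 0.5 and 0.7, equal between all visit pairs, with no missing data. The effect patterns are illustrations.

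**The plan's own figures.** SAP 17.4.2.2 contains no computed figure. The sample size reproduces: a two-sample t-test needs 85.03, so 86 per arm or 172. Then 86 × (1 − 0.49²) = 65.35, so 66, and 66/0.9 = 73.3, so 74 per group or 148. The adjusted SD is 20 × √(1 − 0.49²) = 17.43.

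**1. Drop rule.** Suppose the true differences fall evenly: 10, 6.7, 3.3, 0. With participant correlation modelled, 66 per arm and rho = 0.5, simulation (3,000 runs) gives p < 0.05 for the interaction in about 93% of trials. Obeying the inequality would then report one pooled effect of about 5 points, (10 + 6.7 + 3.3 + 0)/4. Obeying the word would keep the interaction.

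**2. Linear time.** Code the visits x = −1.5, −0.5, 0.5, 1.5, so Σx² = 5. The fitted difference is mean + slope × x, with slope = Σxd/5.

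- True 10, 2, 0, 0: mean 3.0; slope = (−15 − 1)/5 = −3.2; fitted 7.8, 4.6, 1.4, −1.8.
- True 10, 2, 2, 2: mean 4.0; slope = (−15 − 1 + 1 + 3)/5 = −2.4; fitted 7.6, 5.2, 2.8, 0.4.
- True linear decline: fitted without bias.

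**3. Centre as the only random effect, taken literally.** For the average over four visits, the true variance is proportional to (1 + 3·rho)/4, while the model assumes 1/4. Type I error is therefore 2 × [1 − Φ(1.96/√(1 + 3·rho))]. For a visit-specific contrast, the model assumes 1/4 + x²/5, and the truth is (1 + 3·rho)/4 + (1 − rho)·x²/5. Coverage follows from the square root of the ratio. At rho = 0.5:

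- Weeks 30 and 42: √(0.30/0.65) = 0.679, so coverage is 81.7%.
- Weeks 18 and 54: √(0.70/0.85) = 0.907, so coverage is 92.5%.

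| rho | Pooled SE, stated/true | Pooled type I error | 95% CI coverage, weeks 30 and 42 | 95% CI coverage, weeks 18 and 54 | Size of interaction test |
|---|---|---|---|---|---|
| 0.3 | 0.725 | 15.5% | 86.7% | 93.5% | 1.9% |
| 0.5 | 0.632 | 21.5% | 81.7% | 92.5% | 0.6% |
| 0.7 | 0.568 | 26.6% | 77.3% | 91.4% | 0.03% |

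The last column is 2 × [1 − Φ(1.96/√(1 − rho))]. Simulation under no effect agrees: pooled type I error 16.3%, 22.5% and 27.4% with independent residuals, against 5.2%, 5.3% and 5.8% when the participant is the unit.

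**4. How the parts combine.** With independent residuals the interaction test is too conservative. For 10, 2, 2, 2 at rho = 0.5 it detects the interaction in about 38% of trials, against 70% with participant correlation modelled. A corrected drop rule would then remove a real interaction more often and leave the pooled effect, whose interval is the worst affected.

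**The case against.** The strongest reply is that the paragraph is loosely worded rather than wrong.

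- **The rule.** Its words run in the usual direction, it is permissive, and the bracket reads like shorthand for the 5% level. A reader might infer that the interaction will be dropped exactly when the effect changes over time; that requires following the symbol against the word. This part of the reply stands. It does not rescue the pre-test.
- **Participant term.** A reader might infer that four scores from one patient will be counted as four independent patients. The SAP calls the model repeated-measures and mixed, which ordinarily implies within-participant correlation. The term is unstated, not shown to be absent, so the table above is conditional. Nor are the intervals far too narrow everywhere: with the interaction kept, weeks 18 and 54 are only mildly affected.
- **Trajectory.** A reader might take the Protocol's remark "though surgical intervention could lead to quicker recovery" to mean that an early difference closing by 12 months is expected here. That background passage compares surgery with conservative management, not with TFESI. No trajectory between the two trial arms is stated.
- **Continuous time has a reason.** SAP 17.4.2.2 admits measurements taken off schedule, SAP 17.4.1.1 derives completion dates, and the Protocol's last window runs from 54 to 62 weeks. This is fair, but actual time does not require a straight line.
- **Small biases.** In the 10, 2, 0, 0 example the week-54 value of −1.8 is within noise: its true SE at rho = 0.5 is √(2 × 17.43²/66 × 0.85) = 2.8. This too stands; the example shows direction, not a likely false claim.

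**Conclusion.** The point holds as a defect of specification in the secondary analyses. The drop rule contradicts itself and, once corrected, still conflicts with the separate week 30, 42 and 54 endpoints and with the week-18 estimates required for four outcomes. That conclusion rests on the text alone.

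The other two parts are conditional. Linear time biases visit-specific effects only if the treatment difference is not linear over weeks 18 to 54. Too-narrow intervals arise only if the participant term is really omitted; pooled type I error is then about 15% to 27% for assumed rho 0.3 to 0.7, and visit-specific coverage at rho = 0.5 is about 82% at weeks 30 and 42 and 92.5% at weeks 18 and 54. The 93% chance of a significant interaction and the 21.5% type I error at rho = 0.5 belong to different models and should not be combined.

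The documents do not support saying that the secondary results will be wrong; they could be. Nor do they support saying that a week-18 ODQ effect could be hidden, because that analysis is a separate regression. The primary analysis and the sample size are unaffected. The paragraph should be corrected before the analysis, but it does not threaten the main result.

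**What to change.** Rewrite SAP 17.4.2.2, so that the four cross-referring sections inherit the change:

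1. Delete the drop rule and always retain treatment by time.
2. Fit nominal visit as a four-level factor, and assign off-schedule questionnaires to their scheduled visit under a stated rule. Alternatively, keep actual time and add curvature terms with their treatment interactions.
3. State an unstructured within-participant covariance, or at least a participant random intercept, in addition to centre.
4. Report the treatment contrast with its 95% CI at each visit. Week-18 ODQ stays with the primary regression.

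The cost is one paragraph and a few lines of code. Replacing one linear time term with a four-level factor adds two time terms and two interaction terms, with a small loss of precision. No new data are needed.
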